**Table 2.2-2: Dose Levels for Palbociclib**

Dose Level	Oral Dose	Frequency
Starting dose	125 mg	QD × 3 weeks on (1 week off)
First dose reduction	100 mg	QD × 3 weeks on (1 week off)
Second dose reduction	75 mg	QD × 3 weeks on (1 week off)
Third dose reduction	Discontinue	Not applicable

Abbreviations: mg = milligram; QD = once daily.

### **Randomized Phase**

Once enrolled in IRT, enrolled participants who have met all eligibility criteria will be ready to be randomized through IRT in a 4:4:3 ratio to treatment Arm A, B or C, respectively.

- 1) Arm A (concurrent palbociclib treatment arm): nivolumab 480 mg Q4W IV + palbociclib 125 mg QD PO for 3 weeks (1 week off) + anastrozole 1 mg QD PO for 5 cycles
- 2) Arm B (phased palbociclib treatment arm):
  - a) palbociclib 125 mg QD PO for 3 weeks of each cycle (1 week off) + anastrozole 1 mg QD PO for 1 cycle followed by
  - b) nivolumab 480 mg Q4W IV + palbociclib 125 mg QD PO for 3 weeks (1 week off) + anastrozole 1 mg QD PO for 4 cycles
- 3) Arm C (control palbociclib arm): palbociclib 125 mg QD PO for 3 weeks of each cycle (1 week off) + anastrozole 1 mg QD PO for 5 cycles

The randomization will be stratified by the following factors:

- Evaluation of lymph nodes (cytologically positive vs radiologically or cytologically negative)
- Tumor size (> 3 cm or ≤ 3 cm)

The exact procedures for using the IRT will be detailed in the IRT manual.

### **2.3 Blinding and Unblinding**

This is an open-label study. Blinding procedures between participants and investigators are not applicable.

## 2.4 Protocol Amendments

Document	Date of Issue	Summary of Change
Revised Protocol 03	13-Mar-2020	Closed the abemaciclib safety run-in Cohort 1 and removed the abemaciclib-containing combinations from the randomization phase. Removed eligibility criteria based on RECIST 1.1 as it has been covered by inclusion criteria 2.a.i. Added further instructions on unidimensional measurement for response assessment using ultrasound and mammogram as modifications. Incorporated Administrative Letter 01 and Germany specific amendment.
Revised Protocol 02	24-Jul-2019	Added men, additional dose-limiting toxicity (DLT) criteria, and early study termination criteria. Updated definition of DLT, inclusion/exclusion criteria, and dose modifications.
Revised Protocol 01	12-Jun-2019	Decreased and clarified the frequency of assessments and sample collections, clarified participant eligibility and stratification, and reduced the dose-limiting toxicity period. These changes were made to reduce participant burden and increase overall feasibility of the study.
Original Protocol	02-May-2019	Not applicable

## 3 OBJECTIVES

[figure not shown]
### 3.1 Primary

**Safety Run-in Phase:** Number of participants with occurrence of DLT.

**Randomized Phase:** To assess RCB 0-I rate by central assessment of palbociclib plus anastrozole with or without nivolumab in all participants with untreated primary BC  $\geq 2$  cm (ER+, HER2-).

### 3.2 Secondary

- To assess the safety and tolerability of palbociclib plus anastrozole with or without nivolumab.
- To assess pCR rate by local assessment of palbociclib plus anastrozole with or without nivolumab in participants with untreated primary BC  $\geq 2$  cm (ER+, HER2-)
- To assess ORR (clinical and radiological [ultrasound (preferred) or mammography]) by Investigator assessment and BCS rate of palbociclib plus anastrozole with or without nivolumab in participants with untreated primary BC  $\geq 2$  cm (ER+, HER2-)

## **4 ENDPOINTS**

### **4.1 Primary Endpoints**

#### **4.1.1 *Dose-limiting Toxicity***

Dose-limiting Toxicity (DLT) is defined as treatment-emergent adverse event (TEAE, graded according to the NCI CTCAE v5.0) that occurs during the first 4 weeks after treatment start and that meets specific criteria. [REDACTED]

#### **4.1.2 *Residual Cancer Burden***

Residual Cancer Burden (RCB) is a continuous index combining pathological measurements of primary tumor (size and cellularity) and nodal metastases (number and size) defined by a point system at surgery (refer to Appendix 7 of protocol [RCB Methods]). RCB is assessed by central assessment at the time of definitive surgery. RCB 0-I rate is defined as number of randomized subjects who achieve a RCB 0 or RCB I divided by the number of all randomized subjects.

### **4.2 Secondary Endpoints**

#### **4.2.1 *Pathological Complete Response, Primary Definition***

Pathological Complete Response (pCR) is defined as the absence of residual invasive cancer on hematoxylin and eosin evaluation of the complete resected breast specimen and all sampled regional lymph nodes following completion of neoadjuvant systemic therapy (ie, ypT0/Tis ypN0 in the current AJCC staging system). Pathological complete response is assessed by the local pathologist at the time of definitive surgery. The pCR rate is defined as number of randomized subjects who achieve a pCR divided by the number of all randomized subjects.

#### **4.2.2 *Objective Response Rate***

Objective Response Rate (ORR) is defined as the number of randomized subjects who achieve a best response of complete response (CR) or partial response (PR) based on investigator assessments (using RECIST v1.1 criteria, by clinical or radiological) divided by the number of all randomized subjects. Best Overall Response (BOR) is defined as the best response, as determined by the investigator (using RECIST v1.1 criteria, by clinical or radiological), recorded between the

[figure not shown]
date of randomization and the date of objectively documented progression per RECIST v1.1 criteria, the date of surgery, or date of subsequent therapy, whichever occurs first. For subjects without documented progression or subsequent therapy before surgery, all available pre-surgery response designations will contribute to the BOR determination. Confirmation of response is not required due to the limited number of planned tumor measurement before surgery.

[figure not shown]
#### **4.2.3 Breast-conserving Surgery Rate**

[figure not shown]
Breast-conserving Surgery (BCS) rate is defined as the number of randomized subjects who undergo BCS after completing the study treatments divided by the number of all randomized subjects.

[figure not shown]
#### **4.2.4 Safety and Tolerability**

Other safety endpoints will include the incidence of deaths, adverse events, serious adverse events, adverse events leading to discontinuation, immune-related adverse events and specific laboratory abnormalities (worst grade) in each treatment group. Toxicities will be graded using the National Cancer Institute (NCI) Common Terminology Criteria for Adverse Events (CTCAE) version 5.0. See details in the IO Core SAP.

[figure not shown]

[figure not shown]

## 5 SAMPLE SIZE AND POWER

A total of approximately 115~136 participants will be treated in the study. Before randomization, approximately 3~24 participants will be treated in the Safety Run-in Phase in each cohort (Cohort 1: nivolumab + abemaciclib + anastrozole for 5 cycles; n = 3~6 per dose level of abemaciclib, and Cohort 2: nivolumab + palbociclib + anastrozole for 5 cycles; n = 3~6 per dose level of palbociclib). At the time of Revised Protocol 03, 2 participants had been treated in Cohort 1 which was subsequently closed for enrollment. Approximately 110 participants are planned to be randomized in this study at a 4:4:3 ratio into Arm A (nivolumab + palbociclib + anastrozole for 5 cycles; n = 40), Arm B (palbociclib + anastrozole for 1 cycle, followed by nivolumab + palbociclib + anastrozole for 4 cycles; n = 40), and Arm C (palbociclib + anastrozole for 5 cycles; n = 30), respectively. No stratification variables will be included for formal analysis; however, participants will be stratified [REDACTED] node status, and tumor size for enrollment [REDACTED].

[figure not shown]

## 6 STUDY PERIODS, TREATMENT REGIMENS AND POPULATIONS FOR ANALYSES

### 6.1 Study Periods

- Baseline period:
  - Baseline evaluations or pre-treatment events will be defined as evaluations or events that occur before the date and time of the first dose of study treatment. Evaluations (laboratory tests, pulse oximetry, vital signs [REDACTED]) on the same date and time of the first dose of study treatment will be considered as baseline evaluations. Events (AEs) on the same date and time of the first dose of study treatment will not be considered as pre-treatment events.
  - In cases where the time (onset time of event or evaluation time and dosing time) is missing or not collected, the following definitions will apply:
    - ◆ Pre-treatment AEs will be defined as AEs with an onset date prior to but not including the day of the first dose of study treatment;
    - ◆ Baseline evaluations (laboratory tests, pulse oximetry, vital signs [REDACTED]) will be defined as evaluations with a date (and time if collected) on or prior to the date of first dose of study treatment.
  - If there are multiple valid observations in the baseline period, then the latest non missing observation will be used as the baseline in the analyses. If multiple observations exist on the latest collection date (and time if collected), the record with the latest data entry date and time will be used. If multiple observations exist on the latest collection date (and time if collected) and data entry date and time, then the first observation is used as baseline, unless otherwise specified.

- ◆ Refer to the study-specific protocol for potential additional baseline evaluations definition such as baseline tumor evaluation, etc.
- Post baseline period:
  - On-treatment AEs will be defined as AEs with an onset date and time on or after the date and time of the first dose of study treatment (or with an onset date on or after the day of

first dose of study treatment if time is not collected or is missing). For subjects who are off study treatment, AEs will be included if event occurred within a safety window of 30 days (or 100 days depending on the analysis) after the last dose of study treatment. No “subtracting rule” will be applied when an AE occurs both pre-treatment and post-treatment with the same preferred term and grade.

- On-treatment evaluations (laboratory tests, pulse oximetry and vital signs) will be defined as evaluations taken after the day (and time, if collected and not missing) of first dose of study treatment. For subjects who are off study treatment, evaluations should be within a safety window of 30 days (or 100 days depending on the analysis) after the last dose of study treatment.

•

## 6.2 Treatment Regimens

### **Treatment group in Safety Run-in Phase (Align with IRT Data Specification):**

Cohort 1 Dose Level 1: Nivo 480mg Q4W + Abema 150mg BID + Anast 1mg QD

Cohort 2 Dose Level 1: Nivo 480mg Q4W + Palbo 125mg QD + Anast 1mg QD

Cohort 2 Dose Level 2: Nivo 480mg Q4W + Palbo 100mg QD + Anast 1mg QD

Cohort 2 Dose Level 3: Nivo 480mg Q4W + Palbo 75mg QD + Anast 1mg QD

Cohort 2 Dose Level 4: Nivo 480mg Q4W + Anast 1mg QD

### **Treatment group in Randomized Phase (Align with IRT Data Specification):**

A: Nivo + Palbo + Anast for 5 cycles

B: Palbo + Anast for 1 cycle + Nivo 4 cycles

C: Palbo + Anast for 5 cycles

Treatment group “as randomized” corresponds to the treatment group assigned by the Interactive Response Technology (IRT) system.

The treatment group “as treated” will be same as the treatment group “as randomized” by IRT unless a subject received the incorrect study treatment for the entire period of treatment, in which case the subject’s treatment group “as treated” will be defined as the incorrect study treatment.

Unless otherwise specified, the safety analysis will be based on the treatment group “as treated”.

[figure not shown]
Unless otherwise specified, the efficacy analysis will be based on the treatment group “as randomized”.

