CBC with Differential, Chemistry Panel, and Endocrine Testing	X		X C1-C2			Must be performed within 3 calendar days prior to dosing for all time points, except C1D1, which does not need to be repeated if performed within 7 days prior to the first dose. See Section 9.4.4 (Clinical Safety Laboratory Assessments) for list of laboratory tests.
Efficacy Assessments						
Clinical Breast Examination	X					Clinical breast examination by palpation of breast and axilla.

Table 2-2: On-treatment Pre-surgery (Neoadjuvant) Procedural Outline (Safety Run-in Phase and Randomized Phase; CA2097A8)

Procedure ^a	Neoadjuvant Treatment ^{b,c} Cycle 1-5 (1 cycle = 4 weeks)				Pre-surgery (within 7 days prior to surgery)	Notes ^d
	Day 1	Day 8	Day 15	Day 22		
Breast and Axilla Ultrasound (Preferred) or Mammogram	C2D22 (as clinically indicated)				X	Breast and axilla ultrasound (preferred) or mammogram to be done on C2D22 and within 7 calendar days prior to surgery. Every attempt should be made to image each participant using an identical imaging modality and acquisition protocol for all imaging time points.
Documentation of Actual Breast Surgery	See Notes.					Record actual type of BC surgery (ie, BCS, mastectomy) on day of or within 7 days after surgery.

Table 2-2: On-treatment Pre-surgery (Neoadjuvant) Procedural Outline (Safety Run-in Phase and Randomized Phase; CA2097A8)

Procedure ^a	Neoadjuvant Treatment ^{b,c} Cycle 1-5 (1 cycle = 4 weeks)				Pre-surgery (within 7 days prior to surgery)	Notes ^d
	Day 1	Day 8	Day 15	Day 22		
Study Drug						
Randomization	X					First dose to be administered within 3 calendar days following randomization (for Randomized Phase ONLY).
IRT Drug Assignment	X					Register the visit in the IRT for study drug allocation.

Table 2-2: On-treatment Pre-surgery (Neoadjuvant) Procedural Outline (Safety Run-in Phase and Randomized Phase; CA2097A8)

Procedure ^a	Neoadjuvant Treatment ^{b,c} Cycle 1-5 (1 cycle = 4 weeks)				Pre-surgery (within 7 days prior to surgery)	Notes ^d
	Day 1	Day 8	Day 15	Day 22		
Administer Nivolumab 480 mg (Safety Run-in Cohorts and Arms A and B)	X					To be administered Q4W IV. First dose to be administered within 3 calendar days following randomization. 
 • Randomized Phase: • Arm A and Arm B • Starting at C2D1 for Arm B

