**Table 6.3-1: Populations for Analyses**

Population	Description
All Enrolled	All participants who signed an ICF and were registered into the IRT.
All Randomized	All participants who were randomized to any treatment arm in the study. Participants are grouped within the All Randomized population by the treatment to which they were randomized.  This is the primary analysis set for demography, protocol deviations, baseline characteristics, and primary efficacy analyses.
All Treated	All randomized participants who receive at least 1 dose of study drug. Participants are grouped within the All Treated population according to the treatment they actually received. This is the analysis set for all safety analyses and study drug administration.
All Treated from Safety Run-in Phase	All enrolled participants who received at least 1 dose of study drug in the Safety Run-in Phase. Participants are grouped within the All Treated from Safety Run-in Phase population according to the treatment and dose level they actually received. This is part of the analysis set for all safety analysis and study drug administration.
All DLT-Evaluable	All participants treated in Safety Run-in Phase who have discontinued due to a DLT or who have received 1 dose of nivolumab and 75% of accumulative doses of abemaciclib or palbociclib of the cycle, and have completed the 4-week DLT period.
All RCB Evaluable	All Treated participants who have an RCB of 0, I, II, or III from both the Safety Run-in Phase and Randomized Phase.

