Analyses that take into account the multiple occurrences of a given adverse event will be conducted (see [Section 7.6.11](#)). To prepare these analyses, the CRF data will be processed according to standard BMS algorithms in order to collapse adverse event records into unique records based on the preferred term. These data will be presented as the rate per 100 person-years of exposure. These analyses will take into account all on-treatment events (allowing more than 1 event per subject) and the total exposure time. The person-year exposure will be computed as the sum over the subjects’ exposure expressed in years where the exposure time is defined as

- Patients treated in Arm C of randomized phase: (Date of last dose of study treatment - date of first dose of study treatment + 31 days)/365.25, for subject who are off study treatment and were followed for at least 30 days after last dose of study treatment.

- Patients treated in Safety run-in phase and Arm A, B of randomized phase: (Date of last dose of study treatment - date of first dose of study treatment + 101 days)/365.25, for subject who are off study treatment and were followed for at least 100 days after last dose of nivolumab.
- (Last known alive date - date of first dose of study treatment +1)/365.25, for subjects who are still on-treatment or who are off study treatment and were followed less than 30 days in Arm C (or 100 days in Arm A or B) after last dose of study treatment.

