#### Eligibility:

- Subjects without measurable disease at baseline as per investigator, or with measurable baseline primary tumor of < 2 cm in largest diameter
- Subjects with unknown or negative ER
- Subjects with unknown or positive HER2

- Subjects received any treatment, including radiotherapy, chemotherapy, and/or targeted therapy, administered for the currently diagnosed BC prior to enrollment.
- Subjects with baseline ECOG performance status > 1
- Subjects with misclassified stratification factor levels (IVRS vs clinical database; for randomized phase only)

On-study:

- Subjects receiving any concurrent anti-cancer therapy (chemotherapy, hormonal therapy, immunotherapy, standard or investigational agents for treatment of cancer) outside of the protocol-specified neoadjuvant therapy while on study.
- Subjects whose “as treated” arm different than their as randomized arm (subjects who received the wrong treatment for the entire neoadjuvant treatment period, excluding the never treated)

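### SAP 6.2's as-treated rule leaves four of the six full-regimen arm switches in the randomized safety column, because the arms share cycles

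*SAP*

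**What the plan says.** SAP 6.2 lists the randomized regimens as "A: Nivo + Palbo + Anast for 5 cycles", "B: Palbo + Anast for 1 cycle + Nivo 4 cycles" and "C: Palbo + Anast for 5 cycles". The Protocol's Schedule of Activities (Table 2-2) confirms the phased start of nivolumab: "Starting at C2D1 for Arm B".

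SAP 6.2 then sets the as-treated group equal to the randomized group "unless a subject received the incorrect study treatment for the entire period of treatment". Safety (SAP 7.6) and exposure (SAP 7.4) are tabulated by that as-treated group. Efficacy uses the randomized group.

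SAP Table 6.3-1 defines the safety population without the entire-period condition: "Participants are grouped within the All Treated population according to the treatment they actually received". Protocol Table 10.2-1 has the same definition.

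SAP 7.2.1 counts a wrong-arm deviation only for "subjects who received the wrong treatment for the entire neoadjuvant treatment period, excluding the never treated".

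Two analyses set their time window by arm. Person-years in SAP 7.1.1 have one formula for "Patients treated in Arm C of randomized phase" (30 days after last dose) and another for Arms A and B and the run-in (100 days). Concomitant medication in SAP 7.4.3 has the same split.

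**The concern.** An entire-period test works when arms differ throughout treatment. These arms overlap by design and differ only in nivolumab. A participant can receive another arm's whole regimen and still have had one or more cycles that matched the assigned arm. Under SAP 6.2 that participant is not moved; under the population tables in both documents the participant is. A programmer has to choose between the two rules, and the results differ.

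Arm C is the only nivolumab-free reference in the trial. If an exposed participant stays in that column, any immune event in that person is shown as occurring without nivolumab. In the other direction, an unexposed participant left in Arm B dilutes a nivolumab column. Because SAP 7.2.1 uses the same test, these switches also drop out of the programmed deviation summary.

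**Working it through.** **Inputs.** Nivolumab by cycle, from SAP 6.2 and Protocol Table 7.1-2 (1 = planned, 0 = not):

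- Arm A: 1,1,1,1,1
- Arm B: 0,1,1,1,1
- Arm C: 0,0,0,0,0

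Palbociclib and anastrozole are the same in all arms. Arm sizes (SAP 5) reproduce: 110 × 4/11 = 40, 110 × 4/11 = 40, 110 × 3/11 = 30.

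**Test applied.** A participant moves only if every cycle received differs from the assigned cycle.

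**Full five-cycle switches.**

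| Assigned → received | Cycles that differ | Share of period | Nivolumab doses, planned → received | Moved? |
|---|---|---|---|---|
| A → B | 1 | 1/5 = 20% | 5 → 4 | No |
| B → A | 1 | 1/5 = 20% | 4 → 5 | No |
| B → C | 2-5 | 4/5 = 80% | 4 → 0 | No |
| C → B | 2-5 | 4/5 = 80% | 0 → 4 | No |
| A → C | 1-5 | 5/5 = 100% | 5 → 0 | Yes |
| C → A | 1-5 | 5/5 = 100% | 0 → 5 | Yes |

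Four of six switch types (67%) stay in the randomized column. Under the population-table definition all six would move.

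**Shorter treatment.** The result is the same for two, three or four cycles. If treatment ends after Cycle 1, an A-B switch is wrong throughout and is moved, and Arms B and C cannot be told apart.

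**Partial crossovers.** Over five cycles there are 2^5 − 1 = 31 nivolumab patterns that deviate from a given arm. One of them is wrong in every cycle, so 30 stay. For Arm B that one pattern (nivolumab in Cycle 1 only) matches no other arm, so the rule moves the participant without a column to go to.

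**Weight of one participant.** 1/30 = 3.3 percentage points in Arm C; 1/40 = 2.5 points in Arm A or B. One event wrongly shown in Arm C changes 0/30 (exact 95% CI 0 to 11.6%) to 1/30 (0.1 to 17.2%).

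**Windows.** In SAP 7.1.1 the person-year formula adds 31 days for Arm C and 101 days for Arms A and B, for participants followed for the full window. The label therefore changes exposure time by up to 101 − 31 = 70 days per participant. The immune-mediated, other-special-interest and pneumonitis/ILD tables (SAP 7.6.8 to 7.6.10) use 100 days for every group and do not depend on the label.

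**The case against.** The strongest reply is that SAP 6.2 lists whole-course regimens just above the rule. An Arm C participant given regimen B throughout could then be said to have had the incorrect study treatment for the whole course, and all six switches would move. That reading is possible. But the rule is framed by the period of treatment, SAP 7.2.1 repeats that framing, and neither place says that regimens are compared as wholes. A programmer comparing dosing records with the assigned arm cycle by cycle would get the table above. The whole-regimen reading also leaves partial crossovers unresolved.

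Second, errors would be visible elsewhere. SAP 7.4.1 summarizes the number of nivolumab doses by group and provides a by-subject dosing listing. SAP 7.2.1 sends non-programmable relevant deviations to listings. Protocol 9.3 has dosing errors recorded on the eCRF. This stands as partial mitigation, but listings do not correct the safety tables.

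Third, such errors may be rare. Drug allocation goes through IRT, and a full C-to-B switch needs four infusions given against allocation. This stands too and limits the point's importance.

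A reader might infer that the immune-mediated and pneumonitis tables cut Arm C off at 30 days. They do not; only person-years and concomitant medication are arm-keyed among the analyses above. Protocol 9.2.1 and 9.2.2 do limit event collection to 30 days for participants randomized to Arm C, but footnote a of Protocol Table 2-3 requires follow-up for at least 100 days after the last nivolumab dose. Missing data for an exposed Arm C participant are therefore possible, not certain.

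**Conclusion.** The point holds as a conflict between definitions that gives a wrong safety grouping in identifiable cases. On the plain wording, and with at least two cycles of treatment, four of six full-regimen switches keep the randomized label, contrary to the population tables in both documents. The B/C switches matter most because they put nivolumab-exposed people in the control column (3.3 points each) or unexposed people in Arm B (2.5 points each). A-B switches are minor: both columns are nivolumab columns and the difference is one dose.

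Three stronger conclusions are tempting and not supported:

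- **That most crossovers will be misfiled.** Four of six counts switch types. If destinations were equally likely, (20 + 40 + 15)/110 = 68% would stay, but that pattern is an assumption. The share could be anything from 0% (only full A-C swaps) to 100% (none).
- **That an A-B switch can never be moved.** It is moved if treatment ends after Cycle 1.
- **That nivolumab toxicity will be materially hidden.** The documents give no error rate, and it may be low.

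Efficacy, including the primary RCB 0-I analysis, is unaffected because it follows randomization. The change should be made before database lock, because choosing between the two rules afterwards, with open-label data in view, would be hard to defend.

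**What to change.** 1. **SAP 6.2.** Define as-treated as the arm whose regimen was actually received over the cycles treated, determined by whether nivolumab was received and whether it was given in Cycle 1. Apply this to all six switches, including A to B. State that omissions and early stopping permitted by the Protocol do not change the group.
2. **Isolated erroneous doses that match no arm's schedule.** Keep the randomized arm, flag and list the participant, and footnote in the safety tables any events after that dose.
3. **SAP 7.2.1.** Count as a deviation any cycle in which nivolumab was given or withheld by error, contrary to the assigned arm.
4. **SAP 7.1.1 (person-years) and 7.4.3 (concomitant medication).** Key the 30- or 100-day window to whether nivolumab was received.

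The cost is SAP wording and one derived variable, plus a judgement for each affected participant on whether a missed dose was an error or a permitted omission. A few participants may sit in different groups for safety and efficacy, which the population tables already allow.
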